The coronavirus disease 2019 (COVID-19), caused by the novel severe acute respiratory syndrome coronavirus 2 (SARS-CoV-2), has caused more than 120 million cases and 2.6 million deaths to date, since 2020. As the pandemic spread, there has been a growing recognition of neuro-psychiatric (NP) impact of COVID infections. Such complications have been described during the acute phase of the infection with emerging data showing that, particularly in severe cases of COVID-19 infection, the acute viral infection is associated with delirium, confusion, and psychosis, possibly related to the cytokine storm (Rogers et al. 2020). Importantly, a much larger proportion of even mild COVID-19 cases experience neuropsychiatric complications at follow-up. Six months after clinical recovery, an estimated 34% of COVID-19 survivors are diagnosed with new-onset neuropsychiatric disorders, in particular anxiety disorders (17%), mood disorders (14%), substance use disorders (7%) and insomnia (5%) (Taquet et al., 2021). It is clear that long COVID NP symptoms threaten the quality of life and the societal functioning of a significant proportion of the active population (De Lorenzo et al., 2020; Ma et al., 2020; Mazza et al., 2020; Varatharaj et al., 2020, Gennaro et al, 2021). It is estimated that this will severely impact the health of patients infected with COVID-19, long after the pandemic will have ended thanks to vaccination efforts. Despite the major socio-economic consequences of the long-term impact of the pandemic, a standardized way to screen, diagnose, predict and specifically treat patients who develop or will develop these NP symptoms is currently not available. Despite post-viral or post-infectious neuropsychiatric symptomatology has been recognized and studied prior to the COVID-19 pandemic, crucial knowledge about the neurobiological mechanisms underlying these symptoms is still lacking.

Large population cohort studies have replicated the finding of systemic immune disturbances in cohorts of patients with depression. Among post-COVID NP patients, baseline systemic inflammation (systemic immune inflammatory index: SII= thrombocyte count x neutrophile count / lymphocyte count) predicted severity of depressive psychopathology at the three-months follow-up (Mazza et al, 2021).

Also, long COVID can be regarded as a condition of chronic stress, which could theoretically be associated with disturbances of the hypothalamo-pituitary-adrenal (HPA) axis, although no studies on HPA axis (dys)function in long COVID have been reported yet.

The aims of this study are to describe the standardized evaluation of the psychopathological and neurocognitive function of long COVID patients and their evolution over time; to explore the cross-sectional and longitudinal association

between long COVID symptoms and immunological measures; and to examine the neuro-endocrine (HPA-axis) characteristics of long COVID syndrome.

Three participant groups will be included: 1) long COVID patients with neuropsychological complaints (P), 2) COVID-survivors without persistent complaints (Ca) and 3) healthy volunteers (Cb).

This is a longitudinal study, starting from November 1st 2021. Enrollment will continue for an estimated period of 24 months, depending on the time course of the epidemic curve. Last-patient-in is expected no later than November 1st, 2023. The study will be organized into three work packages (WP1, WP2 and WP3). WP1 includes psychiatric assessments using questionnaires and blood sampling and is the standard WP for every participant. WP2 includes cortisol measurement using saliva sampling for patients and controls from Cb. who do not fulfill specific exclusion criteria (pregnancy, breastfeeding, hormonal therapy with exception of contraceptives, cortisol treatment). Finally, WP3 includes an extensive neurocognitive assessment by a specialized neuropsychologist for both patients and controls from Ca who do not fulfill specific exclusion criteria (sedative medication, pre-existing neurological disease, severe substance abuse, and IQ < 90).

Patients and controls from Ca will be referred mainly by the University Hospital of Antwerp (UZA) and by long COVID patient support groups and enrolled at first visit to UPCD, where follow-up will also take place at 3, 6 and 12 months. WP1 will be performed at each timepoint, while WP2 and WP3 will only be carried out at baseline and 6 months.

Total sample size is estimated on 130 participants.

List of Abbreviations

- ACTH: adrenocorticotrophic hormone
- BACS: brief assessment of cognition in schizophrenia
- BDI: Beck depression index
- Ca: Control group a: COVID-survivors without NP complaints
- CAR: cortisol awakening response
- Cb: Control group b: healthy controls
- CFS: chronic fatigue syndrome
- CNS: central nervous system
- COVID-19: coronavirus disease of 2019
- CRF: corticotropin-releasing factor
- CRP: C-reactive protein
- DNA: deoxyribonucleic acid
- DRUID: driving under the influence of drugs, alcohol and medicines
- EDTA: ethylenediaminetetraacetic acid
- FU: follow-up
- HDL: high-density lipoprotein
- HERV-W-ENV: human endogenous retrovirus-W envelope
- HPA: hypothalamic-pituitary axis
- IFN- γ : interferon gamma
- IL-1 β : interleukin 1- β
- IL-6: interleukin 6
- NESDA: Netherlands Study of Depression and Anxiety
- NP: neuropsychiatric
- PET: positron emission tomography
- P: patient group
- PTSD: post-traumatic stress disorder
- RT-PCR: reverse transcription polymerase chain reaction
- SARS-CoV-2: severe acute respiratory syndrome coronavirus 2
- SII: systemic immune-inflammatory index
- TG: triglycerides
- TNF- α : tumor necrosis factor alpha
- TSPO: translocator protein
- UPCD: Universitair Psychiatrisch Centrum Duffel (University Psychiatry Hospital of Duffel)
- UZA: Universitair Ziekenhuis Antwerpen (University Hospital of Antwerp)

1. Introduction

1.1. Neuropsychiatric consequences following COVID-19

The coronavirus disease 2019 (COVID-19), caused by the novel severe acute respiratory syndrome coronavirus 2 (SARS-CoV-2), has caused more than 183 million cases and 3,96 million deaths to date, since 2020 (1). As the pandemic spread, there has been a growing recognition of neuro-psychiatric (NP) impact of COVID infections. Such complications have been described during the acute phase of the infection with emerging data showing that, particularly in severe cases of COVID-19 infection, the acute viral infection is associated with delirium, confusion, and psychosis, possibly related to the cytokine storm (2). Importantly, a much larger proportion of even mild COVID-19 cases experience neuropsychiatric complications at follow-up. Six months after clinical recovery, an estimated 34% of COVID-19 survivors are diagnosed with new-onset neuropsychiatric disorders, in particular anxiety disorders (17%), mood disorders (14%), substance use disorders (7%) and insomnia (5%) (3). The NICE guidelines have defined acute COVID-19 as signs and symptoms of COVID-19 from the contamination until 4 weeks, ongoing symptomatic COVID-19 from 4 to 12 weeks and post-COVID-19 syndrome for signs and symptoms which persist for more than 12 weeks (4). These long-term post COVID NP symptoms (also referred to as "long COVID", defined as signs and symptoms of COVID-19 after 4 weeks), which are often accompanied by deficits in several cognitive domains (including attention) (5), are unrelated to respiratory insufficiency suggesting independent brain dysfunction. Studies conducted in Italy, Germany, UK and the US found that post COVID NP symptoms seem to affect between 20 to 70% of patients infected with COVID-19 and to last months after respiratory symptoms resolved, suggesting a separate and enduring mechanism (3,6–11). Most strikingly, these NP complications also occur in younger adults with a mild acute COVID-19 presentation (9,10,12).

It is clear that long COVID NP symptoms threaten the quality of life and the societal functioning of a significant proportion of the active population (6,8,13,14). It is estimated that this will severely impact the health of patients infected with COVID-19, long after the pandemic will have ended thanks to vaccination efforts. This may even become a persisting concern if SARS-CoV-2 infection becomes endemic with a pattern analogous to that of flu with Influenza, in particular as the risk of a new neuropsychiatric diagnosis following COVID-19 is 44% greater compared with influenza(3). Despite the major socio-economic consequences of the long-term impact of the pandemic, a standardized way to screen, diagnose, predict and specifically treat patients who develop or will develop these NP symptoms is currently not available. Despite post-viral or post-infectious neuropsychiatric symptomatology has been recognized and studied prior to the COVID-19

pandemic, crucial knowledge about the neurobiological mechanisms underlying these symptoms is still lacking.

1.2. Neurocognitive deficits following COVID-19

Memory and attention problems, reduced information processing and executive dysfunction are among the most frequent complaints of long COVID patients. Specific complaints include concentration difficulties, mental exertion, word finding difficulties, problems with both explicit and procedural memory retrieval (i.e. difficulty completing tasks which used to be "automatic") and problems with planning and organization of daily activities, combined with the subjective experience of "brain fog" (7,15–17).

Scientific evidence is indicating these cognitive deficits are alarmingly widespread among COVID-survivors. In a longitudinal cohort study of 130 Italian patients aged 18-70 years who were assessed with the Brief Assessment of Cognition in Schizophrenia (BACS) (18) at one and three months after acute COVID-19 pneumonia, only 25 patients (19%) showed equivalent scores within the normal range in all cognitive domains (i.e., verbal memory, verbal fluency, working memory, selective attention, processing speed, psychomotor coordination and planning and problem solving), whereas 21 (16%) were poor performers in at least one function, 22 (17%) in two, 18 (14%) in three, 14 (11%) in four, 7 (5%) in five, and 2 (1.5%) demonstrated deficits in all domains (7).

In the study carried out by Miskowiak et al. (17) cognitive functioning was assessed in a group of 29 Danish COVID-patients approximately three to four months after hospitalisation by means of the Screen for Cognitive Impairment in Psychiatry (SCIP) and the Trail Making Test. Fifty-nine % of the patients showed cognitive deficits (38% was globally impaired and 21% was selective impaired), with verbal memory and executive functions being most affected. Ortelli et al. (16) investigated cognitive functions by means of the MOCA, the FAB and three computerized attentive tasks (the vigilance task, the Stroop interference task and the Navon task) in a group of 12 Italian COVID-survivors approximately 9 to 13 weeks from onset of infection. In comparison with a healthy control group, the patient group showed a significant reduced global cognitive functioning (MOCA and FAB) and significant more problems with vigilance and executive attention (computerized attentive tasks).

In the study of Mazza et al. (2121), the presence of psychopathology (mainly depressive symptomatology) was shown to significantly influence neurocognition in post-COVID patients, most notably affecting verbal fluency, information processing, and executive functions at one and/or three months assessments. Patients' sex,

previous psychiatric diagnosis, and duration of hospitalization for COVID-19 did not significantly affect the neurocognitive function (7).

Importantly, preliminary findings of the same research group indicate that the observed cognitive deficits worsen between three- and six-month follow-up (Figure 1, unpublished data). Furthermore, the neurocognitive profile of these patients demonstrates some similarities with patterns observed in depressed patients using the same assessment method. Yet whereas the depressed symptoms of post-COVID NP patients seem to respond well to regular treatment with serotonergic antidepressants, the cognitive symptoms do not.

[figure not shown]

Figure 1: Cognitive profile of post-COVID patients compared to Healthy controls (HC) and depressed patients (MDD) (Mazza et al. 2021, *in prep*) (7)

1.3. Immune disturbances as translational pathways

1.3.1. Systemic immunological disturbance

Large population cohort studies have replicated the finding of systemic immune disturbances (such as but not limited to IL-6 and C-reactive protein (CRP)) in cohorts of patients with depression (19). Longitudinal studies demonstrated the predictive value of these immunomarkers towards clinical outcome and the development of comorbidities such as chronic fatigue, anorexia, insomnia, somatic disease, ... (20–23). Anti-inflammatory agents have been confirmed as valid add-on treatment options to improve depressive symptoms (24). In longitudinal analyses, higher baseline IL-6 levels predicted a subsequent chronic course of depression in women but not in men (25). Similarly, higher baseline IL-6 levels in childhood were associated with depressive and psychotic symptoms at age 18 (26).

Finally, the clinical observation that some patients with long COVID complaints experience an improvement of their NC symptoms following SARS-CoV-2 reinfection or vaccination supports the hypothesis of immune-related pathways involved in the pathophysiology of post-COVID NP complications.

[figure not shown]

Figure 2: Effect of the decrease of systemic inflammation from hospital admission to 3 months follow-up on the pattern of change of depressive symptoms (measured with BDI-13) during follow-up. (7)

1.3.2. HERV-W-ENV reactivation

It is now clear that COVID-19 NP symptoms can persist beyond 6 months post-infection. Within a window of 90 days, 20% of COVID-survivors are diagnosed with a new psychiatric disorder, which increases to 34% after 6 months (3,11). This suggests that a subsequent autonomous response to the initial infection needs to occur. In this context, a very plausible biological candidate has recently been identified. Indeed, very recent results showed that COVID-19 activates the human endogenous retrovirus-W-envelope protein (HERV-W ENV), which is known to induce persistent innate immune responses and cause neurotoxicity and CNS dysfunction (27). HERV-W elements are atypical segments in the human genome originating from retroviruses, which are able to infiltrate the cell nucleus. Although most HERVs are not transcribed, they encode an envelope protein causing inflammation and neurotoxicity (27). HERV-W-ENV was found to be highly expressed in the lymphocytes of acute COVID-19 patients which was correlated with inflammatory markers (Balestrieri et al, 2021).

Importantly, HERV-W-ENV has previously been implicated in some psychiatric disorders, such as schizophrenia and bipolar disorder (27,28), as well as in neurological conditions such as multiple sclerosis. Importantly, in major mood and psychotic disorders, an inflamed subpopulation represented patients in which the pathology involved HERV-W ENV protein and was associated with increased serum pro-inflammatory cytokines (28).

Another recent publication provided a scientific breakthrough in this domain by identifying the pathogenic pathways induced by HERV-W ENV through altered glutamate functioning and to abnormal behavioural patterns (Johansson et al. 2020). Interestingly, this study evidenced the pivotal role of microglial activation in neurotoxicity and, therefore, highlighted a central common point with the consistent findings of microglial activation as measured with TSPO PET imaging in depression (29).

The reactivation of HERV-W-ENV by SARS-CoV-2 in a proportion of COVID-19 survivors may therefore represent the underlying cause of the persistent systemic inflammation and accompanying neuropsychiatric symptomatology.

1.3.3. Hypothalamo-pituitary-adrenal (HPA) axis function

Long COVID can be regarded as a condition of chronic stress, which could theoretically be associated with disturbances of the hypothalamo-pituitary-adrenal (HPA) axis, although no studies on HPA axis (dys)function in long COVID have been reported yet.

The HPA axis is activated by both physical and psychological stressors and ends with the production of cortisol, which participates in the organism's response to stress, in order to mobilize energy from storages throughout the body and to regulate the psychophysiological, immunological and behavioral responses to stress. The HPA axis activity is regulated by cortisol through negative feedback on the hypothalamus and the pituitary, decreasing the secretion of CRF and ACTH respectively (30–33).

Under normal circumstances, cortisol levels vary across the day, with a peak rise following awakening in the morning (the cortisol awakening response or CAR) and a gradual decline throughout the day. In patients with chronic fatigue syndrome (CFS), an attenuated CAR increase and changes in diurnal cortisol slope (DCS) have been found to be important neuro-endocrine correlates.

Taking the chronic stress and the overlapping symptoms of chronic fatigue and exhaustion into account, one could expect a hypofunction of the HPA axis in long COVID, in analogy with the findings in CFS. Furthermore, there may also be an association with cognitive function and with immunological disturbances (34). Also, the neuro-endocrine correlates might be predictive for the recovery and the response to treatment in long COVID patients. Importantly, HPA axis hyperactivity is well-known to be associated with depression (35).

1.4. Insomnia

Genome Wide Association Studies have demonstrated a strong correlation of the genetic risk of insomnia with depression and anxiety (36,37). Furthermore, insomnia has been identified as a primary risk factor for the onset, persistence and relapse of anxiety, depression and PTSD. In a Network Outcome Analysis of 768 individuals without history of depression, *difficulty initiating sleep* was one of only five direct predictors of first-onset major depressive disorder after six years follow-up (38).

Depending on the study methods, in long COVID patients the prevalence of clinically relevant insomnia was estimated between 5% (diagnosis of insomnia disorder in electronic medical records <6m following infection) and 24% (self-rated insomnia symptoms above clinical cut-off at 3-month follow-up). These symptoms could represent an important risk factor in the subsequent development of anxiety and depressive disorders, and a key mechanism underlying cognitive deficits.

2. Research Objectives

- 1) Describe the standardized evaluation of the psychopathological and neurocognitive function of long COVID NP patients and their evolution over time;
- 2) Explore the cross-sectional and longitudinal association between long COVID NP symptoms and immunological measures;
- 3) Define the prevalence and clinical characteristics of insomnia in long COVID NP patients, as well as its correlation to the clinical psychiatric and neurocognitive symptom domains;
- 4) Compare the immunological profile of long COVID NP patients to those of existing cohorts of comparable primary psychiatric conditions and healthy controls;
- 5) To examine the neuro-endocrine (HPA-axis) characteristics of long COVID syndrome

3. Methodology

3.1. Recruitment and study population

Inclusion criteria - patients:

All patients 18-70 years referred to the University Psychiatric Hospital (Campus UZA and Campus Duffel) for psychological and/or cognitive complaints at least >4 weeks following a confirmed diagnosis of COVID-19 infection with a positive PCR test or an antibodies test will be invited to participate in the study. The sample size of the patients is estimated on 50 participants. **The patients have to be examined by their**

treating physician before enrollment to make sure other medical causes for their complaints are excluded. A positive score on at least two domains (psychological / cognitive) is necessary during the screening phase (see 3.3.1).

Inclusion criteria – controls:

Two control groups, one of 30 healthy controls (Cb), another of 50 COVID-19 survivors without persistent complaints (Ca), matched on age, sex and education with the patient group will be included. The participants for Ca will be recruited in UZA and by advertising. The healthy controls (Cb) will be recruited by mailing within the hospital and by advertising. A positive score on maximum one domain (psychological / cognitive) is allowed in the absence of a psychiatric diagnosis (confirmed by the MINI) and when the complaint causes significant distress (which is investigated during the screening phase).

General exclusion criteria:

Participant is unable to read and understand the consent form and patient-reported outcomes, complete study-related procedures, or communicate with the study staff and informed consent cannot realistically be obtained in retrospect or with the help of a competent family member or legal representative.

Exclusion criteria for each subgroup:

- HPA subgroup
 - Participant is pregnant or breastfeeding
 - Participant receives hormonal replacement therapy (contraception is allowed).
 - Participant is treated with cortisol <4 weeks ago
- Neurocognitive assessment:
 - IQ < 90 (screened with Raven Standard Progressive Matrices (Short Form) (RSPM-SF) (39)
 - Participant takes sedative medication
 - Benzodiazepines: Larger than the equivalent of diazepam 10mg per day. Last administration <8 hours prior to the neurocognitive tests.
 - New sedative antipsychotics/antidepressants (<4 weeks)
 - Other medication from DRUID class III (<4 weeks), last administration <8 hours prior to the neurocognitive tests, or causing significant sedation.

- **Severe** substance abuse (alcohol + drugs)
- Pre-existing neurological diseases

[figure not shown]

Figure 3: Flowchart of the COVID-19 participant inclusion and the work packages (WP). Participants with a confirmed positive PCR test will be included at UZA or UPCD and are classified in the patient group when suffering from neuropsychiatric symptoms for more than 4 weeks. All participants undergo psychiatric assessment and blood sampling on every time point of the study (WP1). Additionally, if patients do not fulfill the exclusion criteria for HPA-axis assessment (pregnancy, breastfeeding, treatment with corticosteroids, hormonal replacement therapy with exception of contraceptives), they are included in the cortisol subgroup (WP2). Finally, all participants, except those treated with class III drugs according to the DRUID classification, those suffering from pre-existing neurological disease or substance abuse and those with an IQ below 90, undergo neurocognitive assessment (WP3).

[figure not shown]

Figure 4: Flowchart of the healthy control inclusion and the work packages (WP). Healthy volunteers can be included in Cb if they were not infected with Sars-CoV-2 in the past and if they do not complain from psychic or cognitive symptoms. If they meet the exclusion criteria for the cortisol testing, they are excluded from the study. WP2 is only performed at baseline.

Study design

General study design:

This is a longitudinal study, which will be organized into three work packages (WP1, WP2 and WP3). Enrollment will continue for an estimated period of 24 months, depending on the time course of the epidemic curve. Last-patient-in is expected no later than November 1st, 2023.

Patients will be referred mainly by the University Hospital of Antwerp (UZA) and enrolled at first visit to the University Psychiatric Hospital (UPCD), where follow-up will also take place at 3, 6 and 12 months. Patients can also be referred by the Flemish long COVID patient support group.

Sample size:

Based on current referral rates, we expect on average 1-2 new referrals each week. After 12 months, we expect a total of ± 50 patient inclusions. In a MANOVA analysis, a total sample size of 64 offers 80,0% power to detect a medium sized effect ($f^2 \geq 0.15$). We aim for a total sample size of 130 in order to achieve higher effect sizes and to maintain sufficient power in the subgroup analyses and in case of missing values. As Ca is the main control group for the long COVID patient group, these two groups are of equal size (both 50 participants). We included a smaller Cb group to compare the immunological blood parameters between healthy volunteers and long COVID patients.

Study visits:

As part of routine clinical care, patients will receive psychiatric evaluation at the University Hospital Campus UZA, and neurocognitive evaluation at Campus Duffel. During the clinical evaluations, participants will be invited to participate in the study. If they are interested, they will be invited to a baseline visit assessing eligibility and covering informed consent procedure. In order to adhere to social distancing regulations, it may occur that this baseline visit is held digitally via livestream/webcam or by telephone. In this case, patients sign their ICF digitally. To ensure patient privacy, only in-house fully secured internet and telephone connections will be used for distanced baseline visits.

Once included, the participant will be invited for the baseline assessment, which includes a broad neuropsychological examination. A blood sample will be collected at each time point during the study.

	SCREENING	BASELINE	3 MONTHS	6 MONTHS	12 MONTHS
PATIENT GROUP	Eligibility, psychiatric and IQ screening	Psychiatric assessment Blood sample	Psychiatric assessment Blood sample	Psychiatric assessment Blood sample	Psychiatric assessment Blood sample
+ NC SUBGROUP		Neurocognitive assessment		Neurocognitive assessment	
+ HPA SUBGROUP		Saliva sample		Saliva sample	
CONTROL GROUP A	Eligibility, psychiatric and IQ screening	Psychiatric assessment Blood sample	Psychiatric assessment Blood sample	Psychiatric assessment Blood sample	Psychiatric assessment Blood sample
+ NC SUBGROUP		Neurocognitive assessment			
+ HPA SUBGROUP		Saliva sample			
CONTROL GROUP B	Screening Eligibility, psychiatric screening and IQ screening	Baseline Psychiatric assessment Blood sample Saliva sample	1 month Psychiatric assessment Blood sample	2 months Psychiatric assessment Blood sample	3 months Psychiatric assessment Blood sample

Figure 5: Tasks per (sub)group for each time point of the study

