3.3 Study measurements

To begin with, possible participants will be screened for eligibility before inclusion. First, patients with long COVID symptoms can be referred after completing the screening tests, assessing psychological and cognitive complaints, and can be included if these self-report questionnaires indicate neuropsychiatric symptoms. The control group will perform a screening test to exclude any self-reported psychological or cognitive complaints. If possible, these screening tests will be organized on an online platform.

The data which will be collected for this study which are part of routine clinical practice include the following procedures:

- a baseline clinical psychiatric interview to determine a patient's past and current mental state and psychiatric diagnosis, including psychiatric rating scales
- a baseline neuropsychological evaluation including a standardized test battery (optional)
- extensive neurocognitive tests to examine and document persistent cognitive complaints

Additionally, the following study-related procedures will be performed:

- informed consent and eligibility screening
- blood sample draw (max 35ml per visit)
- saliva cortisol sampling
- additional self-rated scales assessing insomnia, fatigue and psychopathology
- a questionnaire regarding important bio-psycho-social factors such as familial psychiatric antecedents, socio-economic status, social network during the pandemic, personal experience with the COVID-related restrictions, ...

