3.3.3. Blood sampling

Blood samples will be collected in a standardized manner by venipuncture. Two blood vials will be collected and processed to perform the following analyses:

- serum collection tube(s) allowing for HERV-W ENV and serological assays
- plasma collection tubes for the assessment of other immune-related biomarkers (including but not limited to CRP, IL-6, IL-1b, TNF-a, IFN-g, tryptophan, kynurene, 3-OH-kynurene, quinolinic acid, kynurenic acid, enzymes of the kynurene pathway).

A maximum of 35ml blood will be collected during each visit, clinical test sampling included. Study-dedicated blood tubes will be processed for respective plasma and serum extraction according to standardized protocols and plasma / serum will subsequently be stored at -80°C until analysis or elimination.

Residual pellet material of whole blood centrifugation for plasma collection will be utilized for DNA extraction to perform additional genotyping. Emerging evidence has linked specific DNA haplotypes with increased risk of psychiatric morbidity. Exploration of specific immune related genes in post-COVID NP patients might reveal insights in genetic predisposition for infection-driven psychiatric decompensation. DNA sequencing of immune related loci (including but not limited to MHC-II) will be performed on residual pellet material from centrifugated blood collection tubes for plasma procurement if specific additional consent is obtained from the participant. If such consent is not granted, residual pellet material will be discarded after plasma collection.

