3.3.5. Electronic clinical records

The following demographic and clinical variables will be collected through electronic clinical records. If certain data is unavailable from the records, the participant may be contacted by a member of the research team for an additional interview.

- Demographics: age, gender
- Clinical diagnosis at baseline psychiatric evaluation
- Medical history
- Psychiatric history
- Family psychiatric history
- Current + past medication use
- Metabolic parameters: weight, length, waist circumference, triglycerides (TG), HDL-cholesterol, blood pressure, fasting plasma glucose
- Current substance abuse: nicotine, alcohol, cannabis
- If available, results of RT-PCR of SARS-CoV-2 on a nasopharyngeal swab or of SARS-CoV-2 serology
- Date of acute infection, duration of NP symptoms of long Covid
- If available, brain imaging, polysomnography or other technical exams performed during or after COVID-19 infection, including lab results during acute COVID-19 infection
- If available: inflammatory parameters in lab result during acute infection. Otherwise: inflammatory parameters of last clinical lab result (including but not limited to white blood cell count)
- SARS-CoV-2 vaccination status

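### Proof of past infection is defined inconsistently (PCR or an unspecified antibody test in 3.1, PCR only in Figure 3), and no method is named for verifying that Cb were never infected

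*Combined protocol and SAP*

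**What the plan says.** **Patients (P).** Section 3.1 asks for complaints more than four weeks "following a confirmed diagnosis of COVID-19 infection". The proof is given in the words that follow: "with a positive PCR test or an antibodies test will be invited to participate in the study". No antigen, assay or date relative to vaccination is stated.

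**COVID-19 participants in Figure 3.** The caption reads "Participants with a confirmed positive PCR test will be included at UZA or UPCD". It then assigns those with lasting neuropsychiatric symptoms to the patient group, so PCR is the entry rule for everyone on that chart.

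**Recovered controls (Ca).** Section 3.1 describes them as survivors without persistent complaints and gives matching variables, but no rule for proving infection.

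**Healthy controls (Cb).** The Figure 4 caption says "Healthy volunteers can be included in Cb if they were not infected with Sars-CoV-2 in the past". In Figure 5 the screening visit for Cb is listed as "Screening Eligibility, psychiatric screening and IQ screening". Section 3.3 adds: "The control group will perform a screening test to exclude any self-reported psychological or cognitive complaints".

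**Data that bear on infection status.** Section 3.3.3 plans "serum collection tube(s) allowing for HERV-W ENV and serological assays". Section 3.3.5 collects, from records, "If available, results of RT-PCR of SARS-CoV-2 on a nasopharyngeal swab or of SARS-CoV-2 serology", together with the date of acute infection and vaccination status. None of these is tied to eligibility, to group assignment or to a sensitivity analysis, and section 3.5 does not name vaccination status as a covariate.

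**The concern.** Past infection is what separates P and Ca from Cb. A patient referred on an antibody result alone is eligible under section 3.1 and not under Figure 3, so two recruiters following the same protocol could decide differently.

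The antibody route also has a weakness of its own. Vaccination produces antibodies, and recruitment runs from November 2021 to November 2023 in a population whose vaccination status the protocol records. Unless the result can distinguish infection from vaccination, it does not establish exposure.

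On the other side, Cb was added specifically to compare immunological blood parameters with those of long COVID patients (Sample size paragraph; objective 4). Section 1.3.2 proposes that the virus itself reactivates HERV-W-ENV. An unnoticed earlier infection in a Cb participant would therefore bear directly on the mechanism under study.

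**Working it through.** The plan gives no misclassification rate. Its only sample-size figure (64 for 80.0% power at f² ≥ 0.15) does not depend on one, so there is no stated number to reproduce. The check sets the passages side by side and then examines which way an error would act.

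**1. Entry rules by group**

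- P: PCR or an antibody test (3.1); PCR (Figure 3 caption). These conflict.
- Ca: nothing in 3.1; PCR (Figure 3 caption). The rule is missing from the main text.
- Cb: not previously infected (Figure 4 caption); no test or other check described in Figure 5, 3.3 or 3.3.3.

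The antibody route is written for P only.

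**2. Which comparisons depend on infection status**

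- P versus Ca compares symptoms between two groups both meant to have been infected. It is not an infection contrast.
- The mixed models in 3.5 relate symptoms to inflammation or insomnia and contain no infection term.
- P versus Cb and Ca versus Cb do depend on it: immune markers, HERV-W-ENV (baseline only, section 3.4) and cortisol, which Cb provides at baseline only (Figure 4 caption).

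**3. Direction of error in P versus Cb**

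Let m be the share of P never infected and c the share of Cb previously infected. Write the marker means as μ(P,inf), μ(P,un), μ(Cb,inf) and μ(Cb,un). The intended contrast is

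Δ = μ(P,inf) − μ(Cb,un).

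The observed contrast is

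D = (1−m)·μ(P,inf) + m·μ(P,un) − (1−c)·μ(Cb,un) − c·μ(Cb,inf),

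so the bias is

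D − Δ = −m·[μ(P,inf) − μ(P,un)] − c·[μ(Cb,inf) − μ(Cb,un)].

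This reduces to proportional shrinkage, D = Δ·(1−m−c), only if μ(P,un) = μ(Cb,un) and μ(Cb,inf) = μ(P,inf). The protocol's own background argues against both equalities:

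- Patients are selected for symptoms, and section 1.3.1 links depression to IL-6 and CRP. A never-infected patient could have levels as high as an infected one (first term near zero) or higher (contrast inflated).
- For cortisol, section 1.3.3 expects reduced HPA function in long COVID but links depression to hyperactivity. Never-infected depressed patients could pull the P mean up towards the Cb mean or beyond it.
- A previously infected Cb participant has no complaints and so resembles Ca rather than P. The second term is the effect of infection without complaints, which may differ from Δ.

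**4. Grain of the error**

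One person is 1/50 = 2% of P and 1/30 = 3.3% of Cb. How many such people there would be cannot be derived from the documents.

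**The case against.** The strongest reply has four parts.

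**The criterion is more than a test result.** Section 3.1 speaks of a confirmed diagnosis, requires the treating physician to exclude other medical causes, and 3.3.5 records the date of acute infection. A vaccinated person with no illness episode does not fit this naturally, and the word positive may govern both tests. This narrows the risk without removing it: the sentence itself makes PCR or antibodies the means of confirmation, and the infection date is a recorded variable, not an entry condition.

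**Cb are screened for eligibility.** Never having been infected is an eligibility criterion, and the flowchart drawings may show a step that the captions omit. That is fair. The supportable statement is that the captions and running text describe no method of verification, not that none exists.

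**The reach is limited.** Ca is called the main control group, and P versus Ca is not an infection contrast. This stands, and it confines the point mainly to comparisons with Cb.

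**Excluding seropositive Cb could be costly.** In a group of 30, removal could take a large share if unnoticed infection is common. This also stands, and it is why flagging with a sensitivity analysis is preferable to exclusion at entry.

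**Conclusion.** The point holds as an inconsistency plus an uncontrolled risk. Section 3.1 and Figure 3 give different proofs of infection; section 3.1 gives none for Ca; the antibody route as written can admit vaccinated people who were never infected; and no verification is described for Cb. The size is unknown. The conclusion rests on the text as written, the enrolment dates, and the general premise that vaccination yields antibodies.

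A reader might infer three stronger things that the documents do not support:

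- That exposure is in fact misclassified in every group. The documents show only that it may be, and they write the antibody route for P alone.
- That every group contrast is affected. P versus Ca does not contrast infected with uninfected people.
- That the error necessarily pulls contrasts towards zero by the misclassified share. That needs misclassified people to carry the other group's mean, which is doubtful for symptom-selected patients and complaint-free controls. Power losses computed on that basis would be unsupported for the same reason.

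**What to change.** 1. Use one definition of past infection in section 3.1 and Figures 3 and 4, applied to both P and Ca: a positive PCR, or an antibody result that either distinguishes infection from vaccination or is dated before first vaccination. Name the assay.
2. State in section 3.1 how never-infected status is established for Cb. Use the serology already planned in 3.3.3, on baseline serum, to flag Cb participants with infection-specific antibodies.
3. Add to section 3.5 a sensitivity analysis of the comparisons with Cb, restricted to P and Ca with PCR or infection-specific confirmation and to seronegative Cb. Report the numbers flagged in each group.

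**Cost.** Revised eligibility wording, one specified assay on serum already collected, possible loss of some antibody-only referrals, and a smaller Cb, hence less precision, in the sensitivity analysis. Because Cb participants are flagged and not removed, the main comparison keeps all who were enrolled.
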